#### 10. Consent/Accent Form

The parent/legal guardian and participant will be given consent forms (and assent if participant is <14.0 yrs.) to read and sign prior to the participant's entry into the screening and randomization phases, if eligible. The consent and assent forms will be reviewed and approved by the IRB for content and general readability. The forms will provide participants and parents with an overview of the study objectives, a detailed description of all study procedures/evaluations, study medication side effects. The forms will be given to participant, participant's parent/legal guardian by an approved study team member. The forms will be signed by the participant and parent/guardian as well as study team member and witness.

#### 11. Payment and Remuneration

The participating families will receive \$25 for each 24 ABPM performed

### Costs

The following will be paid for by the study: Shipping costs for ABPM and urine biomarker, ABPM analysis, urine biomarker analysis, and Losartan

#### 12. Inclusion of Women and Minorities

The study should include a similar number of males and females, based on the sex of participants with HbSS and SB0 thalassemia seen at the Pediatric Hematology clinic. We expect that most of our participants will be of African descent, given the ethnic distribution of SCD in the United States. We will invite participants of other ethnic backgrounds to participate, if they meet the eligibility requirements for the study.

#### 13. Inclusion of Children

We plan to enroll only children and adolescent patients with SCD ages  $\geq 5$  and  $< 23$  years of age with hypertension.

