### **Rationale for Evaluating Safety of Using an Intensive BP Treatment Strategy**

Current standard of care in our institution is to place pediatric patients on an antihypertensive medication with a goal of reducing BP to <95th percentile based on NHLBI BP Tables for Children and Adolescent. A recent meta-analysis of 11 trials identified intensive blood pressure therapy (BP<50th or 75th percentile) as compared to standard therapy reduced adverse outcomes, most effectively in patients with concomitant proteinuria. [45] Pediatric non-SCD trials using intensive anti-hypertensive therapy guided by 24 hr ABPM resulted in decrease progression to CKD.[46,47] In a large non-SCD pediatric randomized trial of intensive vs. standard therapy for control of 24 hours blood pressure with an ACE Inhibitor, intensive BP control improved renal outcomes and the greatest impact was seen in patients with glomerulopathies.[46] As most SCD patients without renal disease have low BP relative to the black population, a target of 95 percentile BP may be physiologically hypertensive in SCD and intensive BP may be more appropriate. As no prospective anti-hypertensive trials focused on adolescent patients with SCD, it is vital to first conduct a feasibility trial to determine the safety and tolerability of standard and intensive dosing strategies

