## 2.2 Randomized Feasibility Trial-

A randomized feasibility trial of losartan for the correction of abnormal nocturnal blood pressure dipping in adolescent patients with HbSS or SB0 thalassemia 11-22 years of age who have documented hypertensive blood pressure in clinic will be conducted. Participants will be randomized to losartan at doses to maintain clinic BP either <95th percentile (standard dosing strategy) or <75th percentile (intensive dosing strategy). The study will be analyzed using intention to treat for outcomes which will begin immediately after randomization to losartan. Participants will be followed monthly as standard of care with additional research procedures of performing ambulatory blood pressure monitoring at baseline, 3 months, and 6 months and urine/blood biomarkers of kidney injury at baseline, 3 months and 6 months. We propose to identify 60 eligible participants of which 40 will participate in the randomized feasibility trial. The parents/legal guardians of these children will have a one hour educational session on hypertension and kidney disease in sickle cell disease. The parents/legal guardians will be offered the opportunity to discuss hypertension and kidney disease with a Pediatric Nephrologist prior to participation in the trial.

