### 2.2.a. Eligibility for the Feasibility Trial

#### Inclusion Criteria for Pediatric Cohort (Separate IRB approved study-X130312027))

1. Participant must have sickle cell anemia (hemoglobin SS) or sickle  $\beta^0$ -thalassemia (hemoglobin S $\beta^0$ ) as confirmed at the local institution by hemoglobin analysis.
2. Participant must be 5 to 22 years of age (i.e., must not have attained their 23rd birthday).
3. Informed consent in accordance with the institutional policies (institutional IRB approval) and Federal guidelines (approved by the United States Department of Health and Human Services) must be signed by the participant's legally authorized guardian acknowledging written consent to join the study.

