## 2.2.b. Inclusion Criteria for Feasibility Trial Screening

1. Enrolled in Pediatric Cohort Study
2. History of abnormal clinic blood pressure (3 abnormal blood pressure readings (systolic or diastolic) in last 4 visits) as defined by NHLBI Blood Pressure Tables for age and height.
3. History of 1) abnormal nocturnal blood pressure dipping as defined by <10% dip (daytime-nighttime systolic or diastolic blood pressure/daytime blood pressure x 100) or 2) abnormal nocturnal load defined by >25% sleep BP >95th percentile.
4. Informed consent in accordance with the institutional policies (institutional IRB approval) and Federal guidelines (approved by the United States Department of Health and Human Services) must be signed by the participant's legally authorized guardian acknowledging written consent to join the study

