## 2.2.c. Exclusion Criteria for Feasibility Trial Screening

1. Participant with history of angioedema to prior ARB or ACE inhibitor
2. Participants with moderate to severe renal impairment (GFR <60mL/min/1.73m^2)
3. Co-administration of another hypertensive medication
4. History of known bilateral renal artery stenosis, unilateral renal artery stenosis to a solitary kidney
5. Hyperkalemia at time of screening (K>6 mmol/L- non-hemolyzed sample)
6. Pregnancy
7. Current use of lithium, digitalis, warfarin

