## 2.2.d. Inclusion Criteria for Feasibility Trial Randomization

1. Repeat ABPM demonstrating abnormal blood pressure dipping (systolic or diastolic dipping <10%) or abnormal nocturnal load
2. Complete a Survey of Barriers and Facilitators to Enrollment in a Pediatric SCD Hypertension Trial

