### 3. UNDERSTANDING ENROLLMENT

All participants approached to participate in the feasibility trial have consented to the cohort study, but will be asked to complete a survey to identify barriers/facilitators to enrollment in a drug trial. Quantitative surveys questions will include Likert questions to determine barriers/facilitators to participation in this trial using two direction intensity scale (strongly agree, agree, disagree, and strongly disagree. The questionnaire will be piloted among adolescent SCD patients not eligible for the feasibility trial.

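### Section 2.2 sets the trial at ages 11-22, but Section 13 and the criteria admit children from age 5, and at low weight the dosing rule gives both arms the same dose

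*Combined protocol and SAP*

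**What the plan says.** **Age.** Section 2.2 describes the trial population as "adolescent patients with HbSS or SB0 thalassemia 11-22 years of age". The rationale for the intensive strategy points in the same direction, noting "no prospective anti-hypertensive trials focused on adolescent patients with SCD", and so does Section 3: "The questionnaire will be piloted among adolescent SCD patients not eligible for the feasibility trial". Section 13 differs: "We plan to enroll only children and adolescent patients with SCD ages" from 5 up to but not including 23, with hypertension.

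The criteria are the operative text. The first item of 2.2.b is "Enrolled in Pediatric Cohort Study". The cohort's own criterion in 2.2.a is "Participant must be 5 to 22 years of age". The rest of 2.2.b, and the lists headed "Exclusion Criteria for Feasibility Trial Screening" (2.2.c) and "Inclusion Criteria for Feasibility Trial Randomization" (2.2.d), mention neither age nor weight.

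**Dose.** Section 6.1 starts everyone on 25 mg whatever their weight. Section 6.3 allows increases at monthly visits up to 1.4 mg/kg/day or 100 mg/day, with doses rounded to the nearest 25 mg tablet. The arms differ only in the clinic BP target that permits an increase: the 75th percentile (intensive) or the 95th (standard). Section 6.3 does not say whether rounding may carry a dose past the maximum.

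**Use.** Section 9.1 wants the between-arm difference in night-time BP change for planning a definitive trial. Section 9.2 compares the strategies by t-test.

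**The concern.** Staff who screen from the written criteria and staff who follow the design section would decide differently about the same child of 5-10 years. An eligibility rule should not leave that open.

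Younger children are in general lighter, and the arms can separate in dose only if the dose can move. Where 1.4 mg/kg/day leaves no room for a second 25 mg tablet, a tighter BP target changes nothing that the participant receives. Such a participant is randomized to a strategy that cannot be delivered and contributes no contrast to the estimate that the trial is meant to supply. The same rule also leaves the permitted dose unclear for light participants, which is a safety matter in its own right.

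**Working it through.** **The plan's own figures.** The plan states no figure for the weight at which titration becomes possible. Its recruitment figures reproduce: 200 x 0.30 = 60 eligible, 40 of these enrolled, and 40 x 0.90 = 36 completing, which is above 30. They are not in dispute here.

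**Step 1: which ages can enter.**

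| Place | Age range |
|---|---|
| 2.2, design | 11-22 |
| 2.2.a, cohort | 5-22 |
| 2.2.b, trial screening | none stated; inherits 5-22 through cohort membership |
| 2.2.c and 2.2.d | none stated |
| 13 | 5 to under 23, with hypertension |

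Section 13 cannot be set aside as a description of the parent cohort. The cohort criteria do not require hypertension, whereas Section 13 and the trial criteria do. So the written criteria enforce a floor of 5, and nothing in them enforces 11.

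**Step 2: weight at which each dose is first reachable.** Inputs: 25 mg start (6.1); maximum 1.4 mg/kg/day or 100 mg/day, read as whichever is lower (6.3); 25 mg tablets (6.3). With closest-tablet rounding, a dose D is reached when 1.4 x kg reaches D - 12.5. If the maximum is strict, D is reached when 1.4 x kg reaches D.

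| Dose | Closest tablet | Strict maximum |
|---|---|---|
| 50 mg | 37.5/1.4 = 26.8 kg | 50/1.4 = 35.7 kg |
| 75 mg | 62.5/1.4 = 44.6 kg | 75/1.4 = 53.6 kg |
| 100 mg | 87.5/1.4 = 62.5 kg | 100/1.4 = 71.4 kg |

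The first row is the point at issue. Below 26.8 kg (or 35.7 kg) no increase from 25 mg is possible in either arm. For example, at 25 kg the maximum is 1.4 x 25 = 35 mg, which gives 25 mg under both rules.

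**Step 3: how far rounding can exceed the maximum.** At 26.8 kg the closest-tablet dose of 50 mg is 50/26.8 = 1.87 mg/kg/day, and 1.87/1.4 = 1.33, so 33% over. At the 75 mg and 100 mg steps the excess is at most 75/62.5 = 1.20 and 100/87.5 = 1.14 times the maximum, so the first step is the worst.

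**Step 4: the fixed start.** Under a strict maximum, 25 mg exceeds 1.4 mg/kg/day below 25/1.4 = 17.9 kg. Under closest-tablet rounding the rounded maximum is still 25 mg down to 12.5/1.4 = 8.9 kg, so that reading produces no conflict at 17.9 kg.

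**Step 5: effect on the contrast.** Suppose a fraction f of each arm cannot be titrated, with no between-arm effect in them and the full effect in everyone else. The observed difference is then (1 - f) of its value in titratable participants: 90%, 80% or 70% for f of 10%, 20% or 30%. These values of f are assumptions, because the documents give no weights.

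**The case against.** The strongest reply is that the design section is clear. If 11-22 is followed in practice, nothing in the documents shows that any participant would weigh less than 26.8 kg. That stands as a limit on size. It does not answer the conflict, because screening is done against the criteria, and they admit the younger child.

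A second reply is that a comparison of strategies by intention to treat properly includes people whose dose never changes. That also stands in part. The diluted difference misleads planning only if the definitive trial excludes such participants or doses them differently.

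Several stronger readings are tempting but go beyond the documents:

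- A reader might infer that the trial has no minimum age at all. It has one, 5 years, inherited through the cohort.
- A reader might infer that anyone below 17.9 kg starts above the maximum. That follows only if rounding may not exceed the maximum, which 6.3 leaves open.
- A reader might infer that light participants carry no safety information. Between 17.9 and 26.8 kg, 25 mg is 1.4 down to 0.93 mg/kg/day, or 100% down to 67% of the weight-based maximum. That is informative about losartan, though not about the difference between strategies.
- A reader might infer that enforcing age 11 breaks the recruitment target. Section 9.1 describes the 30% as those expected to satisfy the eligibility criteria, and no age split is given, so a shortfall cannot be shown.
- A reader might infer that a weight floor is essential. It would exclude patients, and a finer dose increment could serve instead. A floor of 27 kg would be a poor choice: its one dose step is 50/27 = 1.85 mg/kg/day, 32% above the maximum.

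**Conclusion.** The age conflict is certain on the text: 2.2 says 11-22, Section 13 says from 5, and the criteria enforce only 5. The dosing consequence follows by arithmetic. The arms cannot differ in dose below 26.8 kg under closest-tablet rounding, or below 35.7 kg under a strict maximum. Closest-tablet rounding permits a step up to 33% over the maximum. Under a strict maximum the fixed start is too high below 17.9 kg.

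These results assume that the two limits in 6.3 mean whichever is lower and that the 25 mg rounding applies to the weight-based maximum. How many participants would be affected, and hence how much the between-arm estimate would shrink, cannot be computed from the documents. The pooled change from baseline and the acceptance, adherence and retention estimates do not depend on separation between the arms.

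**What to change.** 1. Add to 2.2.b: *Age 11 to 22 years at screening (has not reached the 23rd birthday).* Change Section 13 to the same range.
2. In 6.3, state that doses are rounded down, so that the daily dose never exceeds 1.4 mg/kg or 100 mg, whichever is lower. Under this rule a participant below 17.9 kg could not be given the 25 mg start in 6.1.

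The cost is small in text: one inclusion line, one corrected sentence and one rounding rule. In practice the eligible pool may be smaller. Lighter participants reach each step later, the first at 35.7 kg instead of 26.8 kg, so participants between those weights lose a step that closest-tablet rounding would have allowed. That is the price of keeping to the stated maximum.

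An age limit does not guarantee a weight. If the sponsor wants every participant to have room for at least one step, a minimum weight of 36 kg (1.4 x 36 = 50.4 mg, so 50 mg fits) or a smaller dose increment would provide it. Either is an option for the sponsor, not a required change.

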## ADHERENCE QUESTIONNAIRE

1. Do you sometimes forget to take losartan?	 Yes  No
2. People sometimes miss taking their medication for reasons other than forgetting. Thinking over the past two weeks, were there any days when you did not give your child his/her losartan?	 Yes  No
3. Have you ever cut back or stopped giving your losartan without telling your doctor because you felt worse	 Yes  No
4. When you travel or leave home, do you sometimes forget to bring along your losartan?	 Yes  No
5. Did you take your losartan yesterday?	 Yes  No
6. When you feel like your blood pressure is under control, do you sometimes stop taking losartan?	 Yes  No
7. Taking a medicine every day is a real inconvenience for some people. Do you ever feel hassled about sticking to your blood pressure treatment plan?	 Yes  No
8. How often do you have difficulty remembering to take all of your medicine?	 Never/Rarely  Once in a while  Sometime  Usually  All the time
9. How many doses have you missed since the last visit?	_____

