## 8. ADHERENCE TO LOSARTAN

### 8.1. Methods for Monitoring Adherence:

Participants will complete a modified Morisky Scale of Adherence and ask open ended questions about adherence (qualitative measure of adherence). Participants will be given a pill bottle of losartan dispensed by a study pharmacist with the number of dispensed pills recorded (1-5 extra pills dispensed each month) by the study monitor (quantitative measure of adherence). Participants will return the pill bottles at each visit and the remaining pills will be counted to determine quantitative adherence to losartan. The study coordinator will place a reminder phone call to participants prior to their clinic appointment. Adherence will be defined as taking at least 80% of losartan doses (23 doses/4 weeks).

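### Items 2 and 3 of the adherence questionnaire are worded wholly or partly for a caregiver, although participants aged 11-22 are to complete it (minor wording error)

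*Combined protocol and SAP*

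**What the plan says.** Section 8.1 names the respondent and the role of the form: "Participants will complete a modified Morisky Scale of Adherence and ask open ended questions about adherence (qualitative measure of adherence". Section 2.2 describes the trial population as "adolescent patients with HbSS or SB0 thalassemia 11-22 years of age". The schedule in section 2.3.b places adherence measures at each of the six monthly visits.

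The questionnaire itself has nine items. Item 1 asks "Do you sometimes forget to take losartan" and item 5 asks "Did you take your losartan yesterday"; both address the person who swallows the tablet. Item 2 asks "were there any days when you did not give your child his/her losartan". Item 3 asks "Have you ever cut back or stopped giving your losartan without telling your doctor because you felt worse". Item 9 asks "How many doses have you missed since the last visit".

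The documents give no separate parent form, no field for who answered, no rule on whether a parent may answer for a minor, and no scoring rule. Quantitative adherence comes from counting returned pills, with adherence defined as at least 80% of doses (section 8.1). A daily dose calendar, and interviews for those who miss more than 20% of doses, are described in section 8.2. Under Objective 3, section 9.2 plans a review of adherence rates over time and of the reasons participants give for good or poor adherence.

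**The concern.** A form that participants complete should be answerable by participants. Item 2 presupposes a respondent who has a child and gives that child the drug. Item 3 shifts between a giver and a taker within one sentence. An adolescent or young adult managing their own tablets has to answer item 2 literally, leave it blank, or guess what was meant, and the data would not show which of these happened.

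What is at stake is information on why doses are missed. Pill counts show how many tablets were not taken but not the reason. Items 2, 3 and 6 are the ones that ask about missing or stopping losartan for reasons other than forgetting, and two of those three are faulty. Item 3 is the only one that asks about cutting back because of feeling worse, which bears on tolerability. Section 9.2 intends to use stated reasons to plan adherence support for the definitive trial, and section 1.1.b lists case report forms among the preparations for that trial, so a faulty form could be carried forward.

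**Working it through.** **1. Who each item addresses**

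| Item | Subject | Fits a self-responding participant? | Fits a parent? |
|---|---|---|---|
| 1, 4, 5, 6 | the person taking losartan | yes | not literally |
| 2 | a caregiver giving it to a child | no | yes |
| 3 | giving, but of the respondent's own drug and because of the respondent's own symptoms | ambiguous | ambiguous |
| 7, 8, 9 | the respondent's own treatment, medicine or missed doses; no child mentioned | yes | not literally |

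Section 8.1 names participants, so the second column but one governs: item 2 does not fit and item 3 is unclear. That is 2 of 9 items. The Enrollment Survey, by contrast, offers a child alternative in most of its statements, so the device needed here already exists in the same document.

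**2. The plan's own adherence figure**

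Inputs from sections 8.1 and 8.2: an 80% threshold given as 23 doses in 4 weeks, and an interview trigger of more than 20% missed, given as 6 doses. At one dose a day, 4 weeks is 28 doses.

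- 0.80 × 28 = 22.4, rounded up to 23 (23/28 = 82.1%; 22/28 = 78.6%).
- 0.20 × 28 = 5.6, rounded up to 6 (6/28 = 21.4%).

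Both figures reproduce. They are stated in doses and do not use the questionnaire, so the wording fault does not reach them.

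**3. Is there a fixed direction of error?**

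The documents give no scoring, so this is an illustration under stated assumptions: one point per non-adherent answer, and the same true non-adherent rate *q* on every item considered.

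*Self-responding participant, item 2.* Let *a* be the share who read it literally and answer No. The reported rate is *q*(1 − *a*), a shift of −*qa*.

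- With *a* = 1 and *q* = 0.1, 0.3, 0.5, the shift is −10, −30 and −50 percentage points, so adherence looks better.
- With *a* = 0 (sensible reinterpretation), the shift is 0. A blank does not produce this shift either.

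*Parent answering literally.* Items 1, 4 and 6 become No, which loses 3*q* points. Item 5 becomes No, which counts as non-adherent and gains 1 − *q*. The net is (1 − *q*) − 3*q* = 1 − 4*q*.

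| *q* | Net change in non-adherent points | Adherence looks |
|---|---|---|
| 0.10 | +0.6 | worse |
| 0.25 | 0 | the same |
| 0.30 | −0.2 | better |
| 0.50 | −1.0 | better |

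The sign changes with the respondent, the reading and *q*.

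**The case against.** The strongest reply is that this is a slip of a few words in a secondary instrument. Section 8.1 calls the form the qualitative measure, and adherence is defined in doses and counted from returned pills. Section 9.2 names no questionnaire score and plans no comparison of the form with the pill count. Item 3 is otherwise addressed to the taker, with only one verb wrong, and item 2 opens with a general remark about missing medication that may lead a participant to the intended meaning. Open-ended questions, the calendar and the interviews also collect reasons. All of this stands, and it is why the point is minor. It does not make item 2 answerable as written.

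Three stronger readings are tempting, and the documents do not support them.

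- A reader might infer that self-reported adherence is biased upward. That needs a rule scoring blank or literal No answers as adherent. None is stated, and step 3 of the working shows that the sign can go either way.
- A reader might put the damage at a quarter of the score, counting two of eight items at one point each. The form has nine items, item 8 has five levels, and no point scheme is given.
- A reader might note that item 2 looks back two weeks while visits are monthly, and conclude that half of each interval goes unasked. Item 9 covers the whole interval for the number of missed doses, as do the pill count and the calendar.

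Nor do the documents say that the respondent changes with age or visit. They only leave open whether a parent may answer for a minor, so the comparability problem is conditional on that.

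**Conclusion.** The form is wrong as written, and the error is minor. For the respondent named in section 8.1, item 2 is mis-addressed and item 3 is ambiguous, at all six visits. Answers on non-adherence for reasons other than forgetting are unreliable as a result. If parents answer for some minors, those answers also cease to be comparable between participants, or between visits where the respondent changes.

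No size or direction of bias can be given, because both depend on who answers, how literally, and on a scoring rule that the plan does not state. The 80% pill-count result is unaffected. The conclusion rests on two assumptions: that the form is used as printed, and that section 8.1 means what it says about participants completing it.

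**What to change.** Reword item 2 to ask whether there were days on which the respondent *did not take your losartan*, and change the verb phrase in item 3 to *stopped taking your losartan*.

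State whether a parent may answer for a minor. If so, add *(your child)* alternatives to every item, following the Enrollment Survey, and record who answered at each visit so that the two kinds of response can be told apart.

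The cost is one form revision and one extra field. Treatment, visits and sample size do not change. If the form is already in use, note the date of the change and report items 2 and 3 separately before and after it.
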